The DSMB is also responsible for maintaining the confidentiality of its internal discussions and activities as well as the contents of reports provided to it. During this application, the DSMB will review cumulative study data to evaluate safety, study conduct, and scientific validity and integrity of the trial. Our approved IRB protocol describes timely reporting requirements by the PI related to any adverse events (AEs), serious adverse events (SAEs) or unanticipated problems (UPs). DSMB members must be satisfied that the timeliness, completeness, and accuracy of the data submitted to them for review are sufficient for evaluation of the nature of the event and the safety and welfare of the study

participants. The DSMB will also assess the performance of overall study operations and any other relevant issues, as necessary. **A letter of support from [name] MD, Director, Medical and Safety Core of the UCSD ADCS, and [name] MD, ADCS Medical Monitor is attached, indicating their readiness to convene and oversee a DSMB for this study.** Nominally, the “primary responsibilities” of this DSMB include:

1. Conducting an initial review of the proposed research protocol, informed consent documents and plans for data safety and monitoring, to assure quality study conduct;
2. Reviewing study procedures to assure quality of study conduct, including SOPs for data management and quality control procedures, and when satisfied, recommend subject recruitment be initiated;
3. Evaluating the quality of the ongoing study conduct by performing quarterly evaluations of the study accrual, compliance with eligibility, participant adherence to study requirements, and accuracy and completeness of data;
4. Considering factors external to the study when relevant information becomes available, such as scientific or therapeutic developments that may have an impact on the safety of the participants or the ethics of the study;
5. Protect the safety of the study participants: recommending appropriate study review or temporary halting for any SAE, and termination due to the occurrence of 3 SAEs (e.g. symptom exacerbation or suicidality associated specifically with MEM treatment), or inability of PI to provide necessary assessment information or to answer study questions;
6. Recommending continuation of ongoing studies at quarterly reviews;
7. Ensure the confidentiality of the study data and the results of monitoring; and,
8. Assist the NIA by commenting on any problems with study conduct, enrollment, sample size, and/or data collection.
9. Considering the overall picture, including need to pursue both primary and appropriate secondary analysis, and making these recommendations during the data analysis phase of the project;
10. Reviewing final results, via DSMB report by PI within 90 days of completion of final study subject.

Inclusion of Women and Minorities

Inclusion of women: Women will be included in this study. One key dependent measure (PPI) exhibits clear sexual dimorphism; previous studies of memantine effects detected **no interactions of sex with drug or diagnosis** for any of the proposed measures of early auditory information processing (PPI, MMN or ASSR). Importantly, it is possible that a significant effect of memantine on auditory processing measures, or an interaction between memantine sensitivity and potential moderating factors (e.g. age, baseline performance, single nucleotide polymorphisms) will be evident in only one or the other sex, or that relationships among specific measures might be sex-specific. Thus, there is a strong rationale for assessing the predicted drug effects in both men and women, to test specific predictions of drug-behavior relationships.

To avoid exposure of any fetus to memantine, subject recruitment is limited to individuals \geq 50 years of age; subjects will be excluded if they are pregnant, nursing, imminently planning pregnancy or have a positive urine pregnancy test on screen day or any test day will be excluded from this study. Second, pre-menopausal women will be tested only in the early follicular phase of their menstrual cycle. Third, female subjects of childbearing potential (defined here as any female who has not had a total hysterectomy and/or bilateral oophorectomy, or who has had a menstrual cycle within the past year) will have urine pregnancy tests on each visit. The pregnancy test is able to detect the pregnancy hormone hCG (Human Chorionic Gonadotropin) in urine. HCG will be measured by a urine "dip-stick" ("Surecheck Early Pregnancy Test"). This test is a midstream format test for the detection of the pregnancy hormone in urine. Fourth, in all subjects of childbearing potential, drug testing will occur within days 1 - 10 of menses onset. Fifth, to participate in this study, females of childbearing potential must agree to use a double-barrier method of contraception when participating in sexual intercourse (regardless of other methods of contraception). If a female of childbearing potential becomes pregnant during the study, the subject will be exited from the study. The investigator will determine whether the subject was exposed to active study drug or placebo, and notify the subject of this information.

Typically, the gender distribution for our studies is roughly equal for men and women. Regarding our most recent San Diego county US Census Bureau statistics, 49.8% of San Diego county's population are women. Within the ADRC, the gender distribution is 55% women.

Inclusion of minorities: Ethnic representation is based on recruitment response, with every effort made to include minority groups. Exclusion criteria are not based on ethnicity. Based on our experience, the following ethnic percentages are expected in the AD patient study sample, based on patient demographics at the UCSD ADRC: Caucasian = 74%; Black, not of Hispanic origin = 3%; Latino = 13%; "Other" (Asian American, Native American) = 10%. Thus, prospective recruitment efforts for this renewal period will attempt to buttress those percentages to be more comparable with the US Census Bureau's percentages for San Diego county (approximately 65% White, 5% African American, 11% Asian American or Pacific Islander, 1% Native American, and 32% reporting of Hispanic or Latino origin; 5% reporting two or more races). This recruitment goal of increasing racial and ethnic minority representation will initially be accomplished through a campaign of advertisements in various media sources (i.e., local newsletters, newspapers, periodicals, and radio) and lectures by the candidate and/or co-investigators to local groups and independent living residential facilities as well as with other outreach efforts targeting racial and ethnic minority senior groups (eg., local chapters of the Advisory Committee on Minority Veterans, California Black Health Network, UCSD ADRC Hispanic Program, etc). Our targeted/planned enrollment table numbers reflect this goal of increasing racial and ethnic minority representation to be more comparable to the UCSD ADRC as well as with the US Census Bureau's statistics for San Diego county.

Any ethnic differences in "MEM-sensitive" vs. "MEM-insensitive" groups recruitment will be explored in post-hoc analyses. The source of recruitment information is recorded for each subject, providing us with ethnic "success rates" for particular means of recruitment. Ethnic representation is then reviewed with annual progress reports. Recruitment efforts are adjusted, based on "success rates" of specific recruitment means, to respond to any significant deviation from the projected ethnic recruitment rates. The UC San Diego Health System is an equal opportunity employer; pursuant to state legislation, the University of California no longer applies affirmative action criteria in the student application process.

Resource Sharing

All biomarker data will be shared with the National Database for Clinical Trials (NDCT) related to Mental Illness, with descriptive and raw data submitted semi-annually, and complete data and analyses within 6 months of study closure, via the Global Unique Identifier (GUID) and Data Dictionary technology. Language will be included in all study consent forms to address this plan.

Budgeting for data management support will account for this activity in the final months of PY5, when experimental activity will be completed (month 57), and effort from research staff will be shifted to support these data sharing requirements at the time when they will be most critical (see “Justification”, [name]).

Results will also be shared via presentations to the relevant scientific community. The PI and Co-PI's are active members of many professional organizations where the proposed science will hold great interest, including the American College of Neuropsychopharmacology, Society of Biological Psychiatry and Society for Neuroscience, and will present data from these studies at the meetings for those societies. When data are ready for peer review, they will be disseminated to the scientific community via publications in high impact journals.

It is anticipated that this application will generate at least five distinct types of “resources”:

1. Raw data, both descriptive and quantitative, will be disseminated as described above;
2. Processed and analyzed data will be disseminated via presentations and data-based publications, as described above;
3. Conclusions will be reached from the above data regarding a range of topics, from new biomarkers to opportunities for new therapeutic interventions in our field, and will be disseminated as #2, above, in addition to higher profile symposia;
4. Conceptual ideas related to “bigger picture” issues, from study design to novel ways to understand treatment algorithms, will be reported in review articles and book chapters;
5. With patient release, all genomic information will be shared with NIH via the procedures and timelines described in the **“NIH Genomic Data Sharing Policy” (NOT-OD-14-124)**.

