Phase 1 and Phase 2 measures will be used to achieve **2 Specific Aims**:

Aim 1. *To assess the acute effects of MEM (0 vs. 20 mg) on measures of early auditory information processing (EAIP) in patients with mild-to-moderate severity AD.* Measures of PPI, MMN and ASSR will be assessed in 88 individuals with mild-to-moderate severity AD after placebo (PBO) and 20 mg MEM po, in a double-blind, randomized order cross-over design. **Hypothesis 1:** Assessed across the full cohort of patients, PPI, MMN and ASSR will be significantly greater after MEM vs. PBO. However, the response to MEM will be heterogeneous: the magnitude of this “MEM effect” (MEM minus PBO) will vary across the dependent measures, and across patients, with some patients demonstrating robust increases in EAIP measures after MEM, and other demonstrating little response or reduced EAIP performance.

Aim 2. *To determine the ability of MEM-induced alterations in EAIP in AD patients to predict their clinical response to MEM.* The magnitude of the “MEM effect” will be calculated for each patient and each EAIP measure. MEM treatment will be initiated and titrated to 10 mg bid in all patients. Clinical severity will be assessed at baseline, 8, 16 and 24 weeks using the ADAS-cog as a primary measure. Analyses will determine whether the MEM effect on some or all EAIP measures moderates the magnitude of the clinical response to MEM. **Hypothesis 2:** Patients exhibiting a larger “MEM effect” on EAIP measures will exhibit a more robust positive clinical response to MEM, compared to patients exhibiting a smaller MEM effect on EAIP measures. This hypothesis will be tested empirically for each of the primary EAIP measures, and for regression-derived composite scores from multiple EAIP measures.

Analyses (linear mixed-effects model) will test the hypothesis (H2) that EAIP MEM sensitivity (in Phase 1) predicts the clinical response to MEM (in Phase 2). Moderating roles of specific variables on MEM sensitivity will be assessed, including demographic/clinical variables, baseline neuropsychological measures and genotypes associated with MEM sensitivity or AD. Source localization will identify anatomical substrates associated with MEM effects on EAIPs, and enable us to test structure- and circuit-based mediation models.

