Of greater relevance to the development of AD therapeutics, our findings show that it is possible to detect robust neurophysiological effects of MEM after a single 20 mg pill. These neurophysiological “signals” reflect the fact that MEM is reaching the brain and acting on neural mechanisms that we know are highly relevant to neurocognition (111). Importantly, as with clinical responses to MEM, while the groups show statistically significant increases in EAIP after MEM, there is **heterogeneity in this MEM response**, with some HS and patients exhibiting robust EAIP increases after MEM, and others showing little change, or even small EAIP reductions (Fig. 3). This heterogeneity is critically important to our ability to identify individuals who are more vs. less sensitive to MEM effects on EAIP, and by extension, to ultimately using biomarkers to stratify patients into subgroups for assessing a differential clinical response to MEM.

Fig. 3. Distributions of “MEM effect” (MEM (20 mg) minus PBO) on EAIP performance, for (L to R): PPI (60 ms), MMN, gamma power and gamma coherence, in HS and SZ patients (pooled, since there were no group differences in MEM effects). This application tests the hypothesis that AD patients defined as “MEM-sensitive” based on these “MEM effects” will exhibit a superior clinical response to MEM in a 24 week trial. Different criteria for “MEM-sensitivity” will be empirically assessed, based on discrete distributional criteria (eg. median split) and continuous (linear mixed-effects model) approaches, and using individual EAIPs vs. composite (weighted) indices (see text).

Conceivably, **AD patients in whom MEM most readily accesses the brain, and positively impacts cognition-relevant brain circuitry as detected by enhanced EAIP, will ultimately be most sensitive to its therapeutic effects**, including its ability to slow cognitive decline and behavioral disturbances in AD. We propose to test this hypothesis in the present application.

We hypothesize that evidence for “MEM sensitivity” that identifies an optimal candidate for MEM treatment will be provided by gains in EAIP in response to a MEM “challenge”. This “personalized medicine” approach

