Specifically, we hypothesize and will test in Aims 1-2 that in AD patients, evidence of MEM-enhanced EAIP will predict a superior clinical response to MEM. Prior to starting a standardized MEM treatment regimen, subjects not currently receiving AD medications will be tested to their EAIP response to placebo or a single pill of MEM (20 mg). They will then be followed clinically during MEM monotherapy, consisting of a titration to a daily dose of 10 mg bid for 24 weeks. Clinical indices will be assessed at baseline, weeks 8, 16 and 24. Clinical responses will then be compared across groups stratified by the magnitude of MEM-enhanced EAIP (Fig. 3), and the relationships of MEM-enhanced EAIP measures to the magnitude of clinical gains will be tested using both discrete (ANOVA) and continuous (linear mixed-effects model) approaches. Secondary analyses will be used to optimize criteria for EAIP "MEM sensitivity", to determine whether EAIP MEM sensitivity also predicts the rapidity and durability (in addition to the magnitude) of MEM's clinical benefits, and whether specific demographic, clinical and genetic factors moderate the predictive strength of MEM EAIP sensitivity. If our hypothesis is supported by these findings, we plan to expand our tests in future applications to include combination therapies (MEM+AChE-I) vs. AChE-I monotherapy, and MCI / early AD patients, with the prediction that combined regimens (but not AChE-I monotherapy) will also produce superior gains among subgroups exhibiting the greatest MEM-enhanced EAIP response. Positive findings in this application may also justify tests with other AD therapeutics for which an acute EAIP-based laboratory biomarker is available.

Summary: Current therapeutics for AD are suboptimal. In particular, clinical response to MEM in AD is variable and modest. One strategy to enhance treatment efficacy is to prospectively identify "drug-sensitive" subgroups, based on the presence of predictive biomarkers for drug response (Fig. 1). MEM enhances neurophysiological measures of EAIP in healthy subjects as well as patients with SZ (Fig. 2). We now propose to determine if greater sensitivity to MEM-enhanced EAIP (Fig. 3) predicts a superior therapeutic impact of MEM in AD patients. This application is thus responsive to **PAR-16-365**, and its specific calls for "**Studies to define and refine the target population...**" and "**Studies that address heterogeneity of response.**"

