C. Approach: This application will test the acute effects of 20 mg MEM (po) on EAIP in patients with mild-to-moderate severity AD (**Mini-Mental State Examination score between 10-22 at screening**), and determine whether sensitivity to MEM-induced changes in primary EAIP measures predicts the clinical response to MEM in these patients over a 24-week trial. The primary clinical outcome measure will be the Alzheimer's Disease Assessment Scale (ADAS-cog) (87), as described below. *Secondary analyses will assess alternate potential biomarkers, alternate outcome measures, and moderating roles of specific patient characteristics (including genotype), as well as the anatomical localization of the MEM-induced changes in EAIP measures.*

Aim 1. *To assess the acute effects of MEM (0 vs. 20 mg) on measures of early auditory information processing (EAIP) in patients with mild-to-moderate severity AD.* Measures of PPI, MMN and ASSR will be assessed in 88 individuals with mild-to-moderate severity AD after placebo (PBO) and 20 mg MEM po, in a double-blind, randomized order cross-over design. **Hypothesis 1:** Assessed across the full cohort of patients, PPI, MMN and ASSR will be significantly greater after MEM vs. PBO. However, the response to MEM will be heterogeneous: the magnitude of this “MEM effect” (MEM minus PBO) will vary across the dependent measures, and across patients, with some patients demonstrating robust increases in EAIP measures after MEM, and other demonstrating little response or reduced EAIP performance.

Aim 2. To determine the ability of MEM-induced alterations in EAIP in AD patients to predict their clinical response to MEM. The magnitude of the “MEM effect” will be calculated for each patient and each EAIP measure. MEM treatment will be initiated and titrated to 10 mg bid in all patients. Clinical severity will be assessed at baseline, 8, 16 and 24 weeks using the ADAS-cog as a primary measure. Analyses will determine whether the MEM effect on some or all EAIP measures moderates the magnitude of the clinical response to MEM. **Hypothesis 2:** Patients exhibiting a larger “MEM effect” on EAIP measures will exhibit a more robust positive clinical response to MEM, compared to patients exhibiting a smaller MEM effect on EAIP measures. This hypothesis will be tested empirically for each of the EAIP measures, and for regression-derived composite scores from multiple EAIP measures.

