Aim 1: Repeated measure (Rm)-ANOVAs will determine whether PPI, MMN and ASSR significantly differ after MEM vs. PBO (Hypothesis 1). Primary variables for each EAIP, as well as exploratory "secondary" measures, are identified above. Based on a recruited sample of 88 total participants, we will have 80% power to detect effect sizes of $d = 0.35$ (small) using a Bonferroni corrected $\alpha = .05/3$ (2-tail). Heterogeneity of response will be characterized using variance components expressed as intraclass correlation coefficients (ICCs).

Aim 2: Linear mixed-effects models regressing change in ADAS-cog outcome scores (at 8, 16, and 24 weeks vs. baseline) onto a fixed effect of group defined by MEM sensitivity will test the hypothesis that patients exhibiting a larger "MEM effect" on EAIP measures will exhibit a larger positive clinical response to MEM. Groups will be defined by a median split of "MEM effect" (MEM minus PBO) on EAIP. Power was estimated using methods described by Hedeker et al. (25) solving for sample size with $\alpha = .05$ (2-tail), test-retest correlations of .50, and 5% attrition at each time point. A sample of 88 total participants provides us with 80% power to detect a medium effect of $d = 0.50$. The primary outcome will be chosen based on effect sizes obtained as part of Aim 1. In exploratory analyses, we will also examine group by time interactions using orthogonal polynomial contrasts. We will also predict change in clinical outcomes as a function of all four candidate biomarkers in order to create an optimal prediction equation. We will perform ROC curve analyses using EAIP MEM sensitivity values as continuous variables and predict clinical improvement after MEM as a discrete outcome (responders vs. non-responders) in order to determine the clinical utility of this approach defined in terms of sensitivity and specificity. Secondary analyses will also be conducted with biomarker groups defined as "MEM-sensitive vs. -insensitive" via specific thresholds for EAIP MEM sensitivity.

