Multiple analytic strategies: The critical test of H2 will utilize both continuous and discrete analyses. Treating EAIP MEM sensitivity as a **continuous variable** will enable us to identify moderating factors (i.e. factors moderating the relationship between EAIP MEM sensitivity and clinical MEM sensitivity) with greater power. By identifying these moderators, and their relative contributions to the biomarker-clinical response relationship, *this continuous approach will potentially be more informative regarding the mechanisms by which EAIP MEM sensitivity is related to MEM's clinical impact*. Compared to ANOVA, a linear mixed-effects model is also relatively less impacted by missing data.

Treating MEM sensitivity as a **discrete variable** will enable us to divide the patient sample via a specific threshold, eg. median split, based on EAIP MEM sensitivity (Fig. 3). Exploratory analyses will test more or less stringent thresholds, aiming to optimize the positive and negative predictive value of this discrete threshold. *This approach has the potential practical value of establishing preliminary criteria for distinct MEM-sensitive and MEM-insensitive clinical subgroups.*

Secondary / Exploratory Analyses: To test H2, we will examine multiple metrics of **EAIP MEM sensitivity**:

1. **primary** measures from each individual EAIP measure (described above);
2. **secondary** composite variable based on these 4 primary measures, generated via multiple regression;
3. **exploratory** measures of EAIP: P3a amplitude and RON (described above).

An underlying premise of H2 is that the neurobiological bases of MEM effects on the Aim 1 EAIP measures share some amount of variance, and hence positive and negative predictive value, with the clinical therapeutic response to MEM in AD. However, MEM effects on these 4 EAIP primary measures likely reflects its actions on (overlapping but) non-identical neural substrates; this is consistent with findings that MEM sensitivities on these measures are positively correlated for some (MEM effects on MMN and ASSR (65)) but not other measures (MEM effects on PPI and MMN (99)). *Which of these primary measures, or composite measure, provides the best prediction of MEM effects on AD-relevant neural substrates, and hence provides the best prediction of MEM's therapeutic sensitivity, is an important empirical question that we will address in Aim 2.*

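### The four-marker prediction equation and the tuned sensitivity thresholds have no planned internal validation, and the composite is neither tied to that equation nor given its own test

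*Combined protocol and SAP*

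**What the plan says.** The composite is part of the test of H2. Specific Aims, Aim 2 has "This hypothesis will be tested empirically for each of the primary EAIP measures, and for regression-derived composite scores from multiple EAIP measures", and C. Approach, Aim 2 repeats this almost word for word: "This hypothesis will be tested empirically for each of the EAIP measures, and for regression-derived composite scores from multiple EAIP measures". Secondary / Exploratory Analyses ranks the composite as the secondary metric and defines it only as a "composite variable based on these 4 primary measures, generated via multiple regression". That line does not say what is regressed on the four measures.

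The Aim 2 paragraph under the statistical tests contains the only four-marker regression that is described: "We will also predict change in clinical outcomes as a function of all four candidate biomarkers in order to create an optimal prediction equation". It does not say whether this equation is the composite, and it fixes neither the outcome scale nor the visit.

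The Fig. 3 caption says that criteria for MEM sensitivity will be assessed "based on discrete distributional criteria (eg. median split) and continuous (linear mixed-effects model) approaches, and using individual EAIPs vs. composite (weighted) indices". It does not say where the weights come from or which test decides for a composite.

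On thresholds, B. Innovation has "Secondary analyses will be used to optimize criteria for EAIP" MEM sensitivity. Multiple analytic strategies calls the search over cut-offs exploratory, "aiming to optimize the positive and negative predictive value of this discrete threshold", and sees its value in preliminary criteria for clinical subgroups. The Aim 2 paragraph adds ROC analyses, to judge clinical utility by sensitivity and specificity.

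The general statistical section covers assumption checks, outliers and missing data. Internal validation is mentioned nowhere.

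**The concern.** An equation or cut-off chosen to fit 88 patients describes those patients better than it will describe the next ones. With a single cohort and no validation step, the accuracy that comes out of the plan is the apparent accuracy. This matters because accuracy is what these analyses are meant to deliver: a judgement of clinical utility and provisional subgroup criteria. The plan also asks which single measure or composite predicts best. A comparison of apparent performance favours the composite, because it has four weights to fit.

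A second problem depends on how the composite is built. If its weights are fitted to clinical change and the score is then entered in the same patients as one variable, the test ignores the fitting and a useless composite will often look predictive.

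**Working it through.** **Inputs from the plan.** N = 88; four primary marker effects; ADAS-cog change at three visits; d = 0.50 at a median split; 80% power, "solving for sample size with $\alpha = .05$ (2-tail), test-retest correlations of .50, and 5% attrition at each time point".

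**Assumptions not in the plan.** Responder rate 50% (30% as a variant); cut-off chosen to maximise PPV + NPV; each group at least 20% of patients; normally distributed markers.

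**1. The plan's own figure.** With 44 per group, compound symmetry 0.5 and a constant group effect, the variance of the three-visit mean is (1 + 2×0.5)/3 = 0.667. Power is 0.819 without attrition, 0.811 if losses start after week 8, and 0.791 if 5% are already lost by week 8. The stated 80% reproduces, so the sample size is not in question.

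**2. Tuned cut-offs: average PPV/NPV** (2,500 runs per case).

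| Case | Apparent | New patients |
|---|---|---|
| One marker, no association, 50% responders | 0.57/0.56 | 0.50/0.50 |
| One marker, no association, 30% responders | 0.36/0.76 | 0.30/0.70 |
| One marker, planned effect, 50% | 0.67/0.67 | 0.60/0.60 |
| Fitted equation, no association, 50% | 0.63/0.63 | 0.50/0.50 |
| Fitted equation, no association, 30% | 0.43/0.80 | 0.30/0.70 |
| Fitted equation, planned effect, 50% | 0.68/0.68 | 0.58/0.59 |

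The planned effect is converted by d = 2×0.798r/√(1 − 0.637r²). With d = 0.5 this gives r² = 0.0924 and r = 0.30. The one-marker rows match what the plan describes. The fitted-equation rows apply only if a cut-off is also tuned on the equation.

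**3. Re-testing a score fitted to clinical change, no true association.** The correlation of the fitted score with the outcome is the multiple R. A one-predictor test at 5% with 86 df (t = 1.988) rejects when R² > 3.952/(3.952 + 86) = 0.0439. For four fitted weights this equals F(4,83) > (0.0439/4)/(0.9561/83) = 0.9535, which has probability 0.4375.

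Simulation with three visits correlated 0.5 gives 0.441 for the continuous score, 0.287 for its median split and 0.052 for the joint 4-df test. An independent run gave 0.439 and 0.285 for the first two, whatever the correlation among markers (0, 0.3 or 0.5). Apparent R² averages 4/87 = 0.046. Apparent AUC would average 0.59, if ROC were run on the fitted equation.

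**4. How well the remedies work.** Sensitivity + specificity of a tuned fitted equation, 400 runs:

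| | Apparent | Repeated 10-fold CV | Bootstrap-corrected | New patients |
|---|---|---|---|---|
| No association | 1.23 | 1.00 | 1.07 | 1.00 |
| Planned effect | 1.31 | 1.14 | 1.19 | 1.15 |

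Under the null the bootstrap leaves (1.07 − 1.00)/(1.23 − 1.00) = 30% of the optimism. Under the planned effect it leaves (1.19 − 1.15)/(1.31 − 1.15) = 25%.

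**5. Power cost of the joint test when one marker carries the whole effect** (noncentral F, n = 88). With R² = 0.0924 and one outcome value per patient, power is 0.841 on 1 df and 0.633 on 4 df. If d = 0.5 is in single-visit SDs and three visits are averaged, d becomes 0.5/√0.667 = 0.61 and R² = 0.135. Power is then 0.955 and 0.835, without attrition.

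**The case against.** Several stronger readings are tempting, and the documents do not support them.

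- *The composite has no outcome and no test.* Too strong. The Aim 2 paragraph names clinical change as the outcome of its four-marker regression, and the Fig. 3 caption names the median split and the mixed model alongside composite indices. What is missing is the link between the two and a composite-specific test.
- *The plan scores the fitted equation in its own patients.* This is an inference from the single cohort. The equation is to be created, but no accuracy figure is promised for it. ROC and threshold tuning are described on MEM-sensitivity values, not explicitly on the equation. A single unfitted marker's AUC carries little fitting optimism.
- *The error rate for H2 is 28-44%.* Only if weights fitted to clinical change are re-tested as one score. The four-predictor model itself has nominal size under its joint test.

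The plan also limits what rests on this work. The composite is secondary, the cut-off search is called exploratory and yields preliminary criteria, the study answers a pilot call, further testing is left to future applications, and no patient is treated by biomarker result.

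These points lower the weight of the concern. They do not remove it: a tuned single-marker cut-off is planned, its predictive values are the aim of the search, and nothing corrects them. The labels also differ, since B. Innovation calls optimising the criteria secondary.

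**Conclusion.** The concern holds in limited form. Accuracy reported for the fitted equation or a tuned cut-off will be apparent and optimistic. For the planned case of one tuned marker the excess is about 0.06-0.07 in each predictive value at 50% responders, both with no association and with the planned effect. It reaches about 0.13 with no association if a cut-off is also tuned on the fitted equation. These sizes rest on the assumed responder rate, tuning criterion and minimum group size.

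The inflated error of about 28-29% or 44% is conditional on how the composite turns out to be built and tested. It should be read as a reason to specify the composite, not as the plan's error rate.

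A reader might infer that the main test of H2 is compromised. It is not: a single marker split at its median has no weights or cut-off fitted to the clinical outcome. The change should be made, but the issue is at secondary and exploratory level.

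**What to change.** In the Aim 2 statistical paragraph and Secondary / Exploratory Analyses:

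1. State whether the composite is the four-marker prediction equation.
2. If it is fitted to clinical change, test it by the joint 4-df test of the four marker effects, or by a permutation test that refits the weights each time.
3. For any fitted equation or tuned cut-off, report R², AUC, sensitivity, specificity, PPV and NPV by repeated cross-validation, with weights and cut-offs re-estimated in every fold. Show the in-sample values beside these, labelled apparent. If the bootstrap is used instead, say that it removes only part of the optimism for tuned cut-offs.

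The primary single-marker median-split analysis needs no change.

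**Cost.** A few lines of R and of plan wording; no new data and no change to N = 88. Reported accuracy will be lower and more variable: the SD of sensitivity + specificity is 0.11 by cross-validation, against 0.07-0.08 apparent. The joint test has less power than one prespecified marker that carries the whole effect: about 63% against 84%, or 83% against 96% on the three-visit reading in step 5. The wording should be settled before clinical outcomes are analysed, while it still counts as prespecified.
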